#### **5. Study Population**

Male/Female participants with Stage IIB or IIC cutaneous melanoma of at least 12 years of age will be enrolled in this study.

Prospective approval of protocol deviations to recruitment and enrollment criteria, also known as protocol waivers or exemptions, is not permitted.

##### **5.1 Inclusion Criteria**

Participants are eligible to be included in Part 1 of the study only if all of the following criteria apply (See Section 6.7 for inclusion criteria for Part 2):

##### **Type of Participant and Disease Characteristics**

1. Male/female participants who are  $\geq 12$  years of age on the day of providing documented informed consent/assent [unless local regulations and/or institutional policies do not allow for participants  $< 18$  years of age to participate; for those sites, the eligible population is  $\geq 18$  years of age] with surgically resected and histologically/pathologically confirmed new diagnosis of Stage IIB or IIC cutaneous melanoma per AJCC 8th edition guidelines.

Note: Participants must have T-stage of T3b, T4a, or T4b (Table 3) with pathologically confirmed negative SLN biopsy, and no evidence of regional (N0) or distant metastatic disease (M0) per AJCC 8th edition guidelines (Appendix 11). Surgical considerations can be found in Appendix 10.

2. Participants must not have been previously treated for melanoma beyond complete surgical resection.

Note: Participants may not have been treated with radiation therapy for their melanoma prior to study entry.

3. No more than 12 weeks may elapse between final surgical resection and randomization. Treatment should start only after complete wound healing from the surgery. If there is a delay of 1 to 7 days exceeding 12 weeks due to unforeseen circumstances, the eligibility should be discussed with the Sponsor and the decision documented. A delay of 1 to 7 days for screening imaging requirements will be allowed if Sponsor has allowed 1-week extension between surgical resection and randomization.

Note: Final surgical resection is defined in this protocol as complete resection of melanoma and a SLN biopsy. If the wide excision is followed by the SLN biopsy (ie, they are not performed at the same time), no more than 12 weeks may elapse between the 2 surgical procedures. If a second wide excision needs to be completed after SLN biopsy, this date will be used to calculate final surgical resection date.

4. Have no evidence of metastatic disease on imaging as determined by investigator assessment. All suspicious lesions amenable to biopsy should be confirmed negative for malignancy.
5. Have a performance status of 0 or 1 on the ECOG Performance Scale at the time of enrollment, LPS score  $\geq 50$  (for participants  $\leq 16$  years old.), or a KPS score  $\geq 50$  (for participants  $> 16$  and  $< 18$  years old). (Appendix 8: Performance Status Scales).
6. Participant must have recovered adequately from toxicity and/or complications from surgery prior to starting study treatment.

Male participants:

7. Removed.

Female participants:

8. A female participant is eligible to participate if she is not pregnant or breastfeeding, and at least one of the following conditions applies:
  - Is not a woman of childbearing potential (WOCBP)

OR

- Is a WOCBP and using a contraceptive method that is highly effective (with a failure rate of  $< 1\%$  per year) or be abstinent from heterosexual intercourse as their preferred and usual lifestyle (abstinent on a long-term and persistent basis) as described in Appendix 3 during the intervention period and for at least 120 days after the last dose of study intervention. The investigator should evaluate the potential for contraceptive method failure (ie, noncompliance, recently initiated) in relationship to the first dose of study intervention.

- A WOCBP must have a negative highly sensitive pregnancy test ([urine or serum] as required by local regulations) within 72 hours before the first dose of study intervention.
- If a urine test cannot be confirmed as negative (eg, an ambiguous result), a serum pregnancy test is required. In such cases, the participant must be excluded from participation if the serum pregnancy result is positive.
- Additional requirements for pregnancy testing during and after study intervention are located in Appendix 3.
- The investigator is responsible for review of medical history, menstrual history, and recent sexual activity to decrease the risk for inclusion of a woman with an early undetected pregnancy.
- Contraceptive use by women should be consistent with local regulations regarding the methods of contraception for those participating in clinical studies.

### **Informed Consent**

9. The participant (or legally acceptable representative if applicable) provides documented informed consent/assent for the study and agrees to DMFS and OS data collection until these study endpoints are reached.
10. The participant provides consent/assent for future biomedical research. However, the participant may take part in the main study without participating in future biomedical research.
11. Have adequate organ function as defined in [Table 1](#). Specimens must be collected within 10 days prior to the start of study treatment.

Table 1 Adequate Organ Function Laboratory Values

System	Laboratory Value
Hematological	
Absolute neutrophil count (ANC)	$\geq 1500/\mu\text{L}$
Platelets	$\geq 100\ 000/\mu\text{L}$
Hemoglobin	$\geq 9.0\ \text{g/dL}$ or $\geq 5.6\ \text{mmol/L}$
Renal	
Creatinine OR Measured or calculated  creatinine clearance (GFR can also be used in place of creatinine or CrCl)	$\leq 1.5 \times \text{ULN}$ OR $\geq 30\ \text{mL/min}$ for participant with creatinine levels $> 1.5 \times \text{institutional ULN}$
Hepatic	
Total bilirubin	$\leq 1.5 \times \text{ULN}$ OR direct bilirubin $\leq \text{ULN}$ for participants with total bilirubin levels $> 1.5 \times \text{ULN}$
AST (SGOT) and ALT (SGPT)	Part 1 $\leq 2.5 \times \text{ULN}$
AST (SGOT) and ALT (SGPT)	Part 2 $\leq 2.5 \times \text{ULN}$ ( $< 5 \times \text{ULN}$ for participants with liver metastases)
Coagulation	
International normalized ratio (INR) OR prothrombin time (PT) Activated partial thromboplastin time (aPTT)	$\leq 1.5 \times \text{ULN}$ unless participant is receiving anticoagulant therapy as long as PT or aPTT is within therapeutic range of intended use of anticoagulants

ALT (SGPT) = alanine aminotransferase (serum glutamic-pyruvic transaminase); AST (SGOT) = aspartate aminotransferase (serum glutamic-oxaloacetic transaminase); GFR = glomerular filtration rate; ULN = upper limit of normal.
 
1 Criteria must be met without erythropoietin dependency and without packed red blood cell (pRBC) transfusion within last 2 weeks.
 
2 Creatinine clearance (CrCl) should be calculated per institutional standard.
 
Note: This table includes eligibility-defining laboratory value requirements for treatment; laboratory value requirements should be adapted according to local regulations and guidelines for the administration of specific chemotherapies.
	

## **5.2 Exclusion Criteria**

Participants are excluded from the study if any of the following criteria apply:

### **Medical Conditions**

1. Has a known additional malignancy that is progressing or has required active antineoplastic therapy (including hormonal) within the past 5 years.

Note: Participants with basal cell carcinoma of the skin, squamous cell carcinoma of the skin, or carcinoma in situ (eg, breast carcinoma, cervical cancer in situ) that have undergone potentially curative therapy are not excluded.

Note: Participants with a history of nonulcerated cutaneous/acral primary melanoma <1 mm in depth with no nodal involvement are allowed in this study. Participants with any previous melanoma that was ulcerated,  $\geq 1$  mm in depth, with nodal involvement, metastasis, or was treated beyond surgical resection (for example, radiation therapy) are not eligible for this study. Participants with synchronous melanomas where lesions not under study are not ulcerated and <1 mm in depth are allowed on the study. Participants with a history of mucosal or uveal melanoma are excluded from this study even if diagnosis and treatment were completed >5 years ago.

2. Has a diagnosis of immunodeficiency or is receiving chronic systemic steroid therapy (in dosing exceeding 10 mg daily of prednisone equivalent) or any other form of immunosuppressive therapy within 7 days prior the first dose of study drug.

Note: The use of inhaled or topical steroids and systemic steroids at physiologic doses of corticosteroids (up to 5 mg/m^2/day prednisone equivalent with maximum dose of 10 mg daily) is allowed on study.

3. If participant received major surgery, they must have recovered adequately from the toxicity and/or complications from the intervention prior to starting study treatment.
4. A WOCBP who has a positive urine pregnancy test within 72 hours prior to randomization (see Appendix 5). If the urine test is positive or cannot be confirmed as negative, a serum pregnancy test will be required.

Note: In the event that 72 hours have elapsed between the screening pregnancy test and the first dose of study treatment, another pregnancy test (urine or serum) must be performed and must be negative in order for participant to start receiving study medication.

### **Prior/Concomitant Therapy**

5. Has received prior therapy with an anti-PD-1, anti-PD-L1, or anti-PD-L2 agent or with an agent directed to another stimulatory or coinhibitory T-cell receptor (eg, CTLA-4, OX-40, CD137).

6. Has received prior systemic anticancer therapy for melanoma including investigational agents.
7. Has received a live vaccine within 30 days prior to the first dose of study drug. Examples of live vaccines include, but are not limited to, the following: measles, mumps, rubella, varicella/zoster (chicken pox), yellow fever, rabies, *Bacillus Calmette–Guérin*, and typhoid vaccine. Seasonal influenza vaccines for injection are generally killed virus vaccines and are allowed; however, intranasal influenza vaccines (eg, FluMist®) are live attenuated vaccines and are not allowed.

**Prior/Concurrent Clinical Study Experience**

8. Is currently participating in or has participated in a study of an investigational agent or has used an investigational device within 4 weeks prior to the first dose of study treatment.

Note: Participants who have entered the follow-up phase of an investigational study may participate as long as it has been 4 weeks after the last dose of the previous investigational agent.

**Diagnostic Assessments**

9. Has severe hypersensitivity ( $\geq$ Grade 3) to any pembrolizumab excipients.
10. Has an active autoimmune disease that has required systemic treatment in past 2 years (ie, with use of disease modifying agents, corticosteroids or immunosuppressive drugs). Replacement therapy (eg, thyroxine, insulin, or physiologic corticosteroid replacement therapy for adrenal or pituitary insufficiency) is not considered a form of systemic treatment and is allowed.
11. Has a history of (noninfectious) pneumonitis that required steroids or has current pneumonitis.
12. Has an active infection requiring systemic therapy.
13. Has a known history of human immunodeficiency virus (HIV) infection. No HIV testing is required unless mandated by local health authority.

PCI [REDACTED]

14. Has a known history of Hepatitis B (defined as Hepatitis B surface antigen reactive) or known active Hepatitis C virus (defined as Hepatitis C virus RNA [qualitative] is detected) infection. No testing for Hepatitis B and Hepatitis C is required unless mandated by local health authority.

PCI [REDACTED]

15. Has a history of active tuberculosis (*Bacillus tuberculosis*).

16. Has a history or current evidence of any condition, therapy, or laboratory abnormality that might confound the results of the study, interfere with the participant's participation for the full duration of the study, or is not in the best interest of the participant to participate, in the opinion of the treating investigator.
17. Has a known psychiatric or substance abuse disorder that would interfere with the participant's ability to cooperate with the requirements of the study.

**Other Exclusions**

18. Removed.
19. Has had an allogeneic tissue/solid organ transplant.

**5.3 Lifestyle Considerations**

No restrictions are required.

**5.3.1 Meals and Dietary Restrictions**

Participants should maintain a normal diet unless modifications are required to manage an AE such as diarrhea, nausea, or vomiting.

**5.3.2 Caffeine, Alcohol, and Tobacco Restrictions**

No restrictions are required.

**5.3.3 Activity Restrictions**

No restrictions are required.

**5.3.4 Pregnancy**

If a participant inadvertently becomes pregnant while on treatment with pembrolizumab, the participant will be immediately discontinued from study treatment. The site will contact the participant at least monthly and document the participant's status until the pregnancy has been completed or terminated. The outcome of the pregnancy will be reported to the Sponsor without delay and within 24 hours if the outcome is a serious adverse experience (eg, death, abortion, congenital anomaly, or other disabling or life-threatening complication to the mother or newborn). The study investigator will make every effort to obtain permission to follow the outcome of the pregnancy and report the condition of the fetus or newborn to the Sponsor. If a male participant impregnates his female partner, the study personnel at the site must be informed immediately and the pregnancy must be reported to the Sponsor and followed as described in Section 8.4.6.

## **5.4 Screen Failures**

Screen failures are defined as participants who consent/assent to participate in the clinical study but are not subsequently randomized. A minimal set of screen failure information is required to ensure transparent reporting of screen failure participants to meet the Consolidated Standards of Reporting Trials (CONSORT) publishing requirements and to respond to queries from regulatory authorities. Minimal information includes demography, screen failure details, eligibility criteria, and any adverse events (AEs) or serious adverse events (SAEs) meeting reporting requirements as outlined in the data entry guidelines.

## **5.5 Participant Replacement Strategy**

A participant who discontinues from study treatment or withdraws from the study will not be replaced.

## **6. Treatments**

Study treatment is defined as any investigational treatment(s), marketed product(s), placebo, or medical device(s) intended to be administered to a study participant according to the study protocol.

Clinical supplies [study treatment(s) provided by the Sponsor] will be packaged to support enrollment. Clinical supplies will be affixed with a clinical label in accordance with regulatory requirements.

### **6.1 Treatments Administered**

The study treatments to be used in this study are outlined below in [Table 2](#).

Table 2 Study Treatments

Study Treatment Name	Dose Formulation	Unit Dose Strength(s)	Dosage Level(s)	Route of Administration	Regimen/ Treatment Period	Use	IMP/ NIMP	Sourcing
Pembrolizumab	Solution for infusion	25 mg/mL vial	2 mg/kg (max. 200 mg) Q3W for pediatric participants ( $\geq 12$ and $< 18$ years old);  200 mg Q3W for adults ( $\geq 18$ years of age)	IV infusion via infusion pump	Part 1: 17 cycles  Part 2: 17 or 35 cycles	Experimental	IMP	Provided centrally by the Sponsor
Saline placebo	Solution for infusion	None	None	IV infusion via infusion pump	Part 1:  17 cycles	Placebo	IMP	Provided locally by the study site, subsidiary, or designee

Definition Investigational Medicinal Product (IMP) is based on guidance issued by the European Commission. Regional and/or Country differences of the definition of IMP/NIMP may exist. In these circumstances, local legislation is followed.
								

All supplies indicated in [Table 2](#) will be provided per the ‘Sourcing’ row depending upon local country operational requirements. Every attempt should be made to source these supplies from a single lot/batch number where possible (eg, not applicable in the case where multiple lots or batches may be required due to the length of the study, etc.).

Refer to Section 8.1.8 for details regarding administration of the study treatment.

All study treatments will be administered on an outpatient basis.

## **6.2 Preparation/Handling/Storage/Accountability**

### **6.2.1 Dose Preparation**

Details on preparation and administration of pembrolizumab are provided in the Pharmacy Manual.

### **6.2.2 Handling, Storage and Accountability**

The investigator or designee must confirm appropriate temperature conditions have been maintained during transit for all study treatment received and any discrepancies are reported and resolved before use of the study treatment.

Only participants enrolled in the study may receive study treatment and only authorized site staff may supply or administer study treatment. All study treatments must be stored in a secure, environmentally controlled, and monitored (manual or automated) area in accordance with the labeled storage conditions with access limited to the investigator and authorized site staff.

The investigator, institution, or the head of the medical institution (where applicable) is responsible for study treatment accountability, reconciliation, and record maintenance (ie, receipt, reconciliation, and final disposition records).

For all study sites, the local country Sponsor personnel or designee will provide appropriate documentation that must be completed for drug accountability and return, or local discard and destruction if appropriate. Where local discard and destruction is appropriate, the investigator is responsible for ensuring that a local discard/destruction procedure is documented.

The study site is responsible for recording the lot number, manufacturer, and expiry date for any locally purchased product (if applicable) as per local guidelines unless otherwise instructed by the Sponsor.

The investigator shall take responsibility for and shall take all steps to maintain appropriate records and ensure appropriate supply, storage, handling, distribution and usage of study treatments in accordance with the protocol and any applicable laws and regulations.

## **6.3 Measures to Minimize Bias: Randomization and Blinding**

### **6.3.1 Method of Treatment Assignment**

Treatment allocation/randomization will occur centrally using an interactive response technology (IRT) system. There are 2 study treatment arms. Participants will be assigned

randomly in a 1:1 ratio to pembrolizumab study treatment or saline placebo study treatment in Part 1.

### 6.3.1.1 Stratification

Treatment allocation/randomization will be stratified according to the following factors:

1. Melanoma T-Stage (Table 3) for adults only
2. A separate stratum for pediatric (age 12-17) participants

Table 3 Melanoma Stage Stratification Table

Melanoma Stage	T-Stage	T-Stage Definition (thickness and ulceration status)
IIB	T3b	>2.0-4.0 mm with ulceration
IIB	T4a	>4.0 mm without ulceration
IIC	T4b	>4.0 mm with ulceration

T-stage of disease as defined by thickness and ulceration status per AJCC guidelines 8th edition

### 6.3.2 Blinding

In Part 1 of this study a double-blinding technique will be used. Pembrolizumab and placebo will be prepared and/or dispensed in a blinded fashion by an unblinded pharmacist or unblinded qualified study site personnel. The participant and the investigator who is involved in the study treatment administration or clinical evaluation of the participants are unaware of the group assignments.

Participants in Part 2 will receive pembrolizumab as open-label treatment.

See Section 8.1.11 for a description of the method of unblinding a participant during the study, should such action be warranted.

### 6.4 Treatment Compliance

Administration of study medication(s) will be administered by the investigator and/or study staff according to the specifications within the Pharmacy Manual. The total volume of study medication infused will be compared with the total volume prepared to determine compliance with each dose administered.

Participants experiencing a greater than 12-week delay between doses due to a pembrolizumab-related AE(s) must be discontinued from treatment.

If there are interruptions in the study intervention schedule, the details of and reason for any interruption of study intervention will be documented in the participant's medical record.

Refer to Section 6.6 for dose modification and toxicity management for irAEs associated with pembrolizumab and for other allowed dose interruptions of pembrolizumab.

## **6.5 Concomitant Therapy**

### **6.5.1 Specific Restrictions**

Medications specifically prohibited in the exclusion criteria are not allowed during the ongoing study. If there is a clinical indication for any medication specifically prohibited, discontinuation from study treatment may be required. The investigator should discuss any questions regarding this with the Sponsor. The final decision on any supportive therapy rests with the investigator and/or the participant's primary physician. However, the decision to continue the participant on study treatment requires the mutual agreement of the investigator, the Sponsor and the participant.

Listed below are specific restrictions or prohibitions for concomitant therapy or vaccination during the course of the study:

- Antineoplastic systemic chemotherapy, immunotherapy or biological therapy not specified in this protocol  
Note: Topical 5-fluorouracil use is allowed prior to enrollment on study. Treatment of skin cancers other than melanoma with any topical anticancer agents may be allowed during follow-up.
- Investigational agents other than pembrolizumab.
- Radiation therapy (See exceptions noted in inclusion and exclusion criteria for Part 2 [Section 6.7]).
- Live or live attenuated vaccines within 30 days before the first dose of study intervention and while participating in the study. Note: Killed vaccines are allowed.
- Systemic glucocorticoids for any purpose other than to modulate symptoms from an ECI that is suspected to have an immunologic etiology. Inhaled or topical steroids are allowed, and systemic steroids at doses  $\leq 5\text{mg}/\text{m}^2/\text{day}$  (maximum allowed 10 mg/day) prednisone or equivalent for pediatric participants ( $\geq 12$  years old and  $< 18$  years old) and  $\leq 10$  mg/day prednisone or equivalent are allowed for adults.

Participants who in the assessment of the Investigator require the use of any of the aforementioned treatments for clinical management should be removed from the study unless otherwise specified above.

All treatments the Investigator considers necessary for a participant's welfare may be administered at the discretion of the Investigator in keeping with the community standards of medical care. All concomitant medication will be recorded on the electronic case report form (eCRF) including all prescription, over-the-counter (OTC) products, herbal supplements, and IV medications and fluids. If changes occur during the study period, documentation of drug dosage, frequency, route, and date should also be included on the eCRF.

All concomitant medications received within 28 days prior to the first dose of study treatment and up to 30 days after the last dose of study treatment should be recorded. Concomitant medications administered 30 days after the last dose of study treatment should be recorded for SAEs and ECIs. ECIs are defined in Section 8.4.7.

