## **7. Discontinuation of Study Treatment and Participant Withdrawal**

### **7.1 Discontinuation of Study Treatment**

Discontinuation of study treatment does not represent withdrawal from the study.

As certain data on clinical events beyond study treatment discontinuation may be important to the study, they must be collected through the participant's last scheduled follow-up, even if the participant has discontinued study treatment. Therefore, all participants who discontinue study treatment prior to completion of the protocol-specified treatment period will still continue to participate in the study as specified in Section 1.3 and Section 8.11.3.

Participants may discontinue study treatment at any time for any reason or be discontinued from the study treatment at the discretion of the investigator should any untoward effect occur. In addition, a participant may be discontinued from study treatment by the investigator or the Sponsor if study treatment is inappropriate, the study plan is violated, or for administrative and/or other safety reasons. Specific details regarding procedures to be performed at study treatment discontinuation are provided in Section 8.1.10.

A participant must be discontinued from study treatment but continue to be monitored in the study for any of the following reasons:

- The participant or participant's legally acceptable representative requests to discontinue study treatment.
- The participant's treatment assignment has been purposely unblinded by the investigator, MSD subsidiary or through the emergency unblinding call center during Part 1 prior to recurrence.
- Interruptions from the protocol-specified treatment plan for greater than or equal to 12 weeks between pembrolizumab doses for nondrug-related or administrative reasons require consultation between the investigator and the Sponsor and written documentation of the collaborative decision on participant management.

- A  $\geq$ 12-week break in pembrolizumab treatment due to a drug-related AE.
- The participant has a medical condition or personal circumstance which, in the opinion of the investigator and/or Sponsor, placed the participant at unnecessary risk from continued administration of study treatment.
- The participant has a confirmed positive serum pregnancy test.

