- Participant with confirmed disease recurrence radiographically and/or by exam with subsequent biopsy while on Part 1 treatment with pembrolizumab or placebo must stop Part 1 study treatment. Participants on Part 1 treatment with placebo can be screened for Part 2 therapy with pembrolizumab.
- Confirmed disease recurrence identified by investigator (radiographically and/or by exam with subsequent biopsy) or confirmed progression per iRECIST if clinically stable during Part 2 treatment outlined in Section 8.11 (exception if the Sponsor approves treatment continuation).
- Any progression or recurrence of any malignancy, or any occurrence of another malignancy that requires active treatment (hormonal and/or antineoplastic therapy).
  - Exceptions to secondary malignancy include basal cell carcinoma of the skin, squamous cell carcinoma of the skin, new nonulcerated primary melanoma  $<$ 1mm in depth with no nodal involvement, or carcinoma in situ (eg, breast carcinoma, cervical cancer in situ) that have undergone potentially curative therapy. Exceptions should be discussed with the Sponsor prior to continuing therapy or remaining in follow-up.
  - Diagnosis of a new primary melanoma  $>$ 1mm or  $<$ 1mm with ulceration will result in discontinuation of therapy in Part 1 or Part 2 and make participant no longer eligible for Part 2 therapy.
  - Investigator may submit a Sponsor consultation form to request a participant be unblinded if the participant develops a second malignancy including a new primary melanoma  $>$ 1mm or  $<$ 1mm with ulceration.
- Noncompliance with study treatment or procedure requirements.
- Discontinuation of treatment may be considered for participants who have attained a confirmed CR and have been treated for at least 8 cycles (at least 24 weeks), receiving at least 2 doses of pembrolizumab beyond the date when the initial CR was declared.
- Recurrent Grade 2 pneumonitis.
- Completion of 17 cycles during Part 1 therapy.

Note: Participants who complete Part 1 therapy are still eligible for Part 2 therapy if they meet Part 2 eligibility guidelines. For any participant who is not able to complete the

required 17 cycles, a notification to the Sponsor is required to determine if it would impact eligibility for entry into Part 2.

- Completion of 17 cycles or 35 cycles with pembrolizumab as assigned in Part 2.

Note: The number of treatments is calculated starting with the first dose.

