### **8.3.5 Pregnancy Test**

All women who are being considered for participation in the study, and who are not surgically sterilized or postmenopausal, must be tested for pregnancy within 72 hours prior to the first dose of study treatment in Parts 1 and 2 of the study. If a urine test is positive or not evaluable, a serum test will be required. Participants must be excluded/discontinued from the study in the event of a positive test result. Repeated Pregnancy test should be performed according to the SoA (Section 1.3) and may be conducted as required by local regulations.

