#### **8.11.3.2 Efficacy Follow-up Visits**

Participants in Part 1 and 2 who complete study treatment or discontinue study treatment for a reason other than disease progression will begin Efficacy Follow-up and should be assessed per respective Part 1 and Part 2 SoA (Section 1.3) until PD to monitor disease status. Every effort should be made to collect information regarding disease status until disease progression, withdrawal of consent, pregnancy, or end of study, whichever occurs first. Information regarding post-study anticancer treatment will be collected if new treatment is initiated.

Participants who are eligible to receive retreatment with pembrolizumab according to the criteria in Section 6.7 will move from Efficacy Follow-up to Part 2 when they experience disease recurrence. Details are provided in the SoA (Section 1.3) for retreatment with pembrolizumab.

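### Three protocol sentences, on pregnancy and on prohibited therapy, end participation or disease-status collection where Section 7.1 stops treatment and keeps following

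*Protocol*

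**What the plan says.** The general rule is in Protocol 7.1. Stopping study treatment is not withdrawal from the study, and the list of reasons is headed "A participant must be discontinued from study treatment but continue to be monitored in the study for any of the following reasons". Two entries matter here: "The participant has a confirmed positive serum pregnancy test" and "any occurrence of another malignancy that requires active treatment (hormonal and/or antineoplastic therapy". The section closes by asking that all SoA visits and procedures be completed for these participants. Section 7.2 names withdrawn consent as the only mandatory ground for withdrawal from the study. On pregnancy, 5.3.4 stops treatment only: "If a participant inadvertently becomes pregnant while on treatment with pembrolizumab, the participant will be immediately discontinued from study treatment".

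Three sentences point the other way.

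- 8.3.5, on pregnancy testing: "Participants must be excluded/discontinued from the study in the event of a positive test result". The next sentence begins "Repeated Pregnancy test should be performed according to the SoA (Section 1.3", so on-study tests are in view as well as screening.
- 8.11.3.2, on efficacy follow-up: "Every effort should be made to collect information regarding disease status until disease progression, withdrawal of consent, pregnancy, or end of study".
- 6.5.1, after five bullets (other antineoplastic systemic therapy, other investigational agents, radiation, live vaccines, systemic glucocorticoids): participants who in the investigator's judgement "require the use of any of the aforementioned treatments for clinical management should be removed from the study unless otherwise specified above". The opening paragraph of the same section says only that discontinuation of study treatment may be required.

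**The concern.** A site holding this protocol can find opposite instructions for the same randomized participant. RFS, DMFS and OS are analyzed in all randomized participants. The primary RFS rule (Protocol 9.6.1.1, Table 8; sSAP 3.6.1.1, Table 1) counts a recurrence or death even after new anticancer therapy. That rule can use only events that are documented. A participant whose assessments stop early is censored at the last disease assessment, and if the reason for stopping is related to prognosis or to treatment, the censoring may be informative.

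RFS is exposed only when the pregnancy or prohibited therapy comes before recurrence. Therapy started because of a recurrence follows the RFS event and cannot cost that endpoint. For DMFS and OS the exposure continues after recurrence.

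**Working it through.** This is a comparison of text; no planned figure is in dispute.

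1. **Pregnancy, 8.3.5 against 7.1.** The first sentence of 8.3.5 concerns tests before the first dose in Part 1 and Part 2, so exclusion is the right consequence at screening. But the sentence also says discontinued from the study, and the repeat tests that follow apply to enrolled participants. For a confirmed positive serum test 7.1 gives a different consequence: treatment stops and monitoring continues. There is also a gap at the start of Part 1. The first dose may follow treatment assignment by up to 3 calendar days (8.1.8), and exclusion criterion 4 requires a new test if 72 hours have passed since the screening test. A test can therefore turn positive after randomization and before dosing, when the participant already belongs to the ITT population.

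2. **Pregnancy, 8.11.3.2 against the other stopping lists.** Section 4.1 follows disease status until metastatic recurrence, withdrawn consent or loss to follow-up. The scan-stopping rules in 8.2.1.2 and 8.2.1.3 do not mention pregnancy either. Only 8.11.3.2 does. It ends disease-status collection; it does not remove the participant from the study and does not stop OS follow-up.

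3. **Prohibited therapy, 6.5.1 against its own opening.** The opening paragraph makes treatment discontinuation possible. The closing sentence makes removal from the study the expected outcome. The phrase *unless otherwise specified above* looks backward: it can reach that paragraph and the exceptions in the bullets, but not 7.1 or 8.11.3.

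4. **The sharpest case.** A participant without recurrence develops a second cancer that needs antineoplastic therapy. Under 7.1 treatment stops and monitoring continues. Under 9.4.1.1 the second cancer is not an RFS event, so the participant remains at risk for one. Under the synopsis, nonstudy cancer treatment leads to DMFS follow-up, and everyone is followed for survival. Under the closing sentence of 6.5.1 the participant is removed.

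5. **What happens after removal.** Sections 8.11.3.3 and 8.11.3.4 let a participant who has been discontinued from the study authorize the site investigator to supply updates on tumor, treatment and overall status. Inclusion criterion 9 obtains agreement to DMFS and OS data collection, and 8.11.4 allows vital-status requests. Later DMFS and OS data would therefore become conditional on authorization. The scheduled assessments that support RFS have no such substitute.

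6. **Design figures.** Using a two-look design with Lan-DeMets O'Brien-Fleming spending and drift √(events/4) × |ln HR|, RFS at 179 events and HR 0.60 has drift √44.75 × 0.511 = 3.42. With the interim at 128 events, power is 0.924, against 0.9190 stated. DMFS gives 0.847 (0.8425 stated) and OS gives 0.809 (0.8050 stated). The stated design reproduces closely, and the wording change alters none of these figures.

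**The case against.** The strongest reply is that the protocol as a whole plainly intends continued follow-up, so no site would apply these sentences literally. The synopsis, 7.1, the SoA survival-status row, 8.11.3.3, 8.11.3.4 and 8.11.4 all support it. Four of the five bullets in 6.5.1 correspond to exclusion criteria, so the opening paragraph arguably governs most of the list. Prohibited therapy as such is not on the 7.1 list. On the excepted second malignancies, 7.1 itself asks for Sponsor discussion before the participant remains in follow-up. And 7.2, which ends scheduled visits, is written for withdrawn consent rather than for removal by a site.

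Most of this stands, and it limits the harm. The ITT definition and Table 8 are not themselves contradicted, since they state who is analyzed and how documented events are coded. But the reply does not reconcile 8.3.5 or 8.11.3.2 with 7.1 on pregnancy, and it leaves 6.5.1 with two different consequences for the same need.

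Two stronger readings are tempting. A reader might infer that DMFS and OS data are lost outright after removal; the authorization route in 8.11.3.3 and 8.11.3.4 does not support that. A reader might also infer that participants given steroids for immune-related events would be removed, mainly on pembrolizumab. The 6.5.1 steroid bullet does exempt only an ECI, and 8.4.7 lists only overdose and one liver-laboratory pattern. But 6.5.2 and Table 4 direct corticosteroids for immune-related events, and Table 4 allows pembrolizumab to resume after the taper. That bullet is a minor drafting point.

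**Conclusion.** The conflict is real and should be corrected. On pregnancy it is firm: 8.3.5 and 8.11.3.2 cannot both be followed with 7.1. On prohibited therapy it rests on 6.5.1's own opening, the general rule and the second-malignancy entry in 7.1, and the synopsis. It is strongest for a second cancer needing antineoplastic therapy.

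The consequence is a risk in site conduct: scheduled disease assessment could end before recurrence, and under 6.5.1 or 8.3.5 later DMFS and OS data could come to depend on authorization. The size cannot be derived, because the documents give no rate of removal, prohibited therapy, second cancer or on-study pregnancy. That pregnancy is rare here is a judgement, not a documented figure. A reader might infer a loss of power, but nothing in the documents quantifies one, and no stated power, event count or boundary is wrong.

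**What to change.** Make four wording changes.

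- **6.5.1, closing sentence.** Replace removal from the study with: *should be discontinued from study treatment unless otherwise specified above or agreed with the Sponsor; the participant remains in the study and is followed for RFS, DMFS and OS per Sections 7.1 and 8.11.3.* Stopping treatment stays the default, so nobody continues study drug by oversight when another anticancer therapy is needed.
- **6.5.1, glucocorticoid bullet.** Extend the exemption to immune-related adverse events managed under Section 6.6.
- **8.3.5.** State that a confirmed positive test before randomization in Part 1 means exclusion from the study, and that one before the first Part 2 dose means no Part 2 treatment. At any later time, including between randomization and the first Part 1 dose, study treatment is withheld or stopped and monitoring continues per 7.1. Part 2 needs its own rule because entry to it involves no randomization.
- **8.11.3.2.** Delete pregnancy from the stopping list, and let imaging be adapted as clinically appropriate.

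The cost is text in the next amendment. No visits are added beyond the existing schedule, and the statistical design is unchanged.
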